8.5 Study Design and Sample Size Calculation

The study is a phase I, single-arm study to establish safety and feasibility of proton-based radiation therapy integrated within adjuvant mFOLFIRINOX for patients with resected PDAC. Patients who have completed 2 cycles of mFOLFIRINOX for resected pancreatic adenocarcinoma will be eligible for enrollment. Proton therapy will occur between cycles 6 and 7.

In dose level 1 (DL1), patients will complete cycle 6 chemotherapy (days 1-3) and then receive 5 days of daily 5 GyE proton therapy on days 15-19 (excluding weekend days) in a 28 day cycle, prior to starting cycle 7 (see Figure 1). In DL2, patients will complete cycle 6 chemotherapy (days 1-3) and then receive 5 days of daily 5 GyE proton therapy on days 8-12 (excluding weekend days) in a 21 day cycle, prior to starting cycle 7. A 3+3 dose-escalation schema will be used, requiring 3-12 patients to be enrolled.

Using a 3+3 dose-escalation design, if 0 of 3 patients experience a dose-limiting toxicity (DLT) at DL1, then 3 patients will then be enrolled in DL2. If 1 of 3 patients experiences a DLT at DL1, then 3 additional patients will be enrolled at DL1. If 2-3 of 3 patients experience a DLT at DL1, then the study is terminated. If 1 of 6 patients experiences a DLT at DL1, then 3 patients will be enrolled at DL2. If 0-1 of 3 patients experiences a DLT at DL2, then 3 additional patients will be enrolled at DL2. If 2-3 patients experience a DLT at DL2, treatment will continue at DL1 until 6 patients are enrolled at DL1. If 0-1 of 6 patients experiences a DLT at DL2, then DL2 is the recommended phase 2 dose and schedule (RP2D). Conversely, if 0-1 of 6 patients experiences a DLT at DL1 AND 2 or greater patients experience a DLT at DL2, then DL1 is the RP2D. All cycles will be 14 days, except cycle 6 which is extended to 28 days in DL1, including the 5 daily doses of PRT on days 15-19 (excluding weekend days), and 21 days in DL2, including the 5 daily doses of PRT on days 8-12 (excluding weekend days).

8.6 Analytic plan for exploratory objectives

8.6.1 The nonparametric Kaplan-Meier method will be used to estimate median RFS.

8.6.2 The nonparametric Kaplan-Meier method will be used to estimate median OS.

8.7 Safety Assessments

8.7.1 The safety of FFX and PRT will be assessed by evaluating study drug exposure, adverse events, serious adverse events, oncology-related events, all deaths, as well as changes in laboratory determinations and vital sign parameters.

8.7.2 A summarization of the number of days and/or cycles subjects were exposed to FFX and PRT will be provided.

8.7.3 Analyses of adverse events (and serious adverse events) will include only "treatment-emergent" events, *i.e.*, those that have an onset on or after the day of the first dose of study drug. Analyses will not include those that have an onset greater than 30 days after the treatment. Treatment emergent adverse events will be summarized by system organ class and preferred term according to the MedDRA adverse event coding dictionary. The percentage of subjects experiencing an adverse event at a given severity, NCI CTCAE toxicity grade, and relationship to study drug will be provided.

8.7.4 The number of subject deaths will be summarized (1) for deaths occurring while the subject was still receiving study drug in this study, (2) for deaths occurring off treatment within 30 days after the last dose of study drug, and (3) for all deaths in this study regardless of the number of days after the last dose of study drug. The relatedness of the deaths to the study drugs will also be provided.

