4.4.2 Medical History

At each visit, the subject's medical history will be reviewed and any changes from baseline will be recorded as an adverse event. On C6D1, any changes observed from the screening assessments, prior to dosing, will be recorded in the subject's medical history. All medications (prescription or over-the-counter, including vitamins and/or herbal supplements) will be recorded beginning with the screening visit and continuing up through the date of the final visit.

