6.1 Adverse Event Assessment

The investigators will monitor each subject for clinical and laboratory evidence of adverse events on a routine basis throughout the study. The investigator will assess and record any adverse event in detail including the date of onset, event diagnosis (if known) or sign/symptom, severity, time course, duration and outcome, relationship of the adverse event to study drug, and any action(s) taken. For serious adverse events not considered “probably related” to study drug, the investigator will provide an “Other” cause of the event. For adverse events to be considered intermittent, the events must be of similar nature and severity. Adverse events, whether in response to a query, observed by personnel, or reported spontaneously by the subject will be recorded. All adverse events will be followed to a satisfactory conclusion.

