6.3 Adverse Event and Toxicity Definitions

6.3.1 Adverse Event

An adverse event (AE) is defined as any untoward medical occurrence in a patient or clinical investigation subject administered a pharmaceutical product and which does not necessarily have a causal relationship with this treatment. An adverse event can therefore be any unfavorable and unintended sign (including an abnormal laboratory finding), symptom, or disease temporally associated with the use of a medicinal (investigational) product, whether or not the event is considered causally related to the use of the product. Such an event can result from use of the drug as stipulated in the protocol or labeling, as well as from accidental or intentional overdose, drug abuse, or drug withdrawal. Any worsening of a pre-existing condition or illness is considered an adverse event. Laboratory abnormalities and changes in vital signs are considered to be adverse events only if they result in discontinuation from the study, necessitate therapeutic medical intervention, and/or if the investigator considers them to be adverse events.

An elective surgery/procedure scheduled to occur during a study will not be considered an adverse event if the surgery/procedure is being performed for a pre-existing condition and the surgery/procedure has been pre-planned prior to study entry. However, if the pre-existing condition deteriorates unexpectedly during the study (e.g., surgery performed earlier than planned), then the deterioration of the condition for which the elective surgery/procedure is being done will be considered an adverse event.

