6.4 Adverse Event Collection Period

All adverse events reported from the time of study drug administration until 30 days following discontinuation of study drug administration have elapsed will be collected, whether elicited or spontaneously reported by the subject. In addition, serious adverse events will be collected from the time the subject signed the study-specific informed consent.

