6.7 Toxicity Management and Dose Adjustments

6.7.1 Dose Reduction and Delays of FFX

As patients will enter the study already having completed 5 cycles of FFX, discretion is given to the investigator to continue patients at the same doses as cycle 5. Therefore, all dose modifications are recommended but left to the discretion of the investigator.

Table 6. Dose Levels for Modifications for FFX (Recommended)

Episode #	Irinotecan	Oxaliplatin	5-FU/LV
1 st	Decrease to 120 mg/m ²	Decrease to 75 mg/m ²	Decrease to 1800 mg/m ²
2 nd	Decrease to 90 mg/m ²	Decrease to 65 mg/m ²	Decrease to 1200 mg/m ²
3 rd	Off Study	Off Study	Off Study

Table 7. Dose Modifications for FFX (Recommended)

Toxicity	Instruction
ANC < 1500/mm ³	Hold until ANC ≥ 1500/mm ³ and reduce one dose level as above
Platelets < 75000/mm ³	Hold until platelets ≥ 75000/mm ³ and reduce one dose level as above
Febrile neutropenia or Grade 4 neutropenia ≥ 7 days	Hold until afebrile and ANC ≥ 1500/mm ³ , reduce one dose level as above
Grade 3-4 diarrhea	Initiate Imodium prn, hold until resolved to baseline or grade 1, reduce one dose level as above
Grade 3-4 peripheral neuropathy	Discontinue oxaliplatin

Other grade 3-4 toxicity	Hold until toxicity resolves to baseline or grade 1, reduce one dose level as above
--------------------------	---

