8.2.1 Median recurrence-free survival (mPFS)

8.2.2 Median overall survival (mOS)

8.3 Primary Endpoint:

The primary endpoint is to determine the RP2D between the 2 proposed schedules. Using a 3+3 dose-escalation schema, 2-12 patients will be required to determine the RP2D.

Co-primary endpoints:

8.3.1 Safety: adverse event data will be collected and presented as descriptive statistics using the CTCAE version 5.0.

8.3.2 Feasibility: we will track the success rate in screening patients, completion of proton beam planning, completion of proton beam treatment, and completion of adjuvant therapy (including number of cycles completed and relative dose intensity).

8.4 Exploratory Endpoints:

8.4.1 Recurrence-free survival (RFS), defined as time from surgery until evidence of disease recurrence.

8.4.2 Overall survival (OS), defined as time from surgery until death from any cause or last follow-up.

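### The adverse event tables select on onset date alone, so a toxicity that predates cycle 6 day 1 and worsens later could be left out if it keeps its pre-dose onset date

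*Combined protocol and SAP*

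**What the plan says.** Section 8.7.3 confines the AE and SAE analyses to treatment-emergent events and equates these with "those that have an onset on or after the day of the first dose of study drug". It also drops events that start more than 30 days after treatment. It has no clause for an event that begins before the first dose and becomes more severe afterwards.

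These analyses carry a co-primary endpoint. Under 8.3.1, "adverse event data will be collected and presented as descriptive statistics using the CTCAE version 5.0", and 8.7.3 reports percentages of subjects by severity, CTCAE grade and relationship.

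Other sections bear on worsening:

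- 6.3.1: "Any worsening of a pre-existing condition or illness is considered an adverse event".
- 4.4.2: at each visit "any changes from baseline will be recorded as an adverse event", whereas on C6D1 "any changes observed from the screening assessments, prior to dosing, will be recorded in the" medical history.
- 6.4: the collection period covers "All adverse events reported from the time of study drug administration until 30 days following discontinuation of study drug administration". SAEs are collected from consent.
- 6.1: each event is recorded in detail, "including the date of onset, event diagnosis (if known) or sign/symptom, severity, time course, duration and outcome".
- 6.7.1: "As patients will enter the study already having completed 5 cycles of FFX".

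**The concern.** Patients reach C6D1 after several cycles of the same chemotherapy that continues on study, so some may arrive with a low-grade toxicity. The question for a trial that adds proton therapy (PRT) is whether such a toxicity becomes severe. A rule that selects on onset date alone counts a grade 3 diarrhoea that is new, but may miss one that grew out of a grade 1 event already on file. Whether it is missed depends on whether the site opens a new entry or extends the existing one. A co-primary result should not turn on that choice. The error can only run one way, because the rule can remove worsened events but cannot add any.

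**Working it through.** The plan states no figure on this point, so the check sets the sections side by side and then shows what one omitted patient would do.

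**1. When is the first dose?** Section 5.1 defines the study drugs as the FFX agents and does not name PRT. Section 4.2.1.11 places the urine pregnancy test at C6D1 ahead of the first study drug dose. Section 4.2.1 makes patients who start on C6D1 eligible for the safety analysis. The implied anchor is C6D1, but 8.7.3 does not say so. If it meant cycle 1 of FFX, toxicities from earlier cycles would pass the filter. If it meant the first PRT dose, events starting between C6D1 and day 8 or day 15 would fail it.

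**2. Can an event with a pre-dose onset be on file?** Yes, by three routes.

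- Tables 2 and 3 schedule an AE assessment at screening and at C6D1. Screening may be up to 28 days before C6D1, and FFX cycles last 14 days. The window can therefore hold 28/14 = 2 cycles of FFX.
- SAEs are collected from consent (6.4).
- Section 6.4 goes by when an event is reported, while 8.7.3 goes by onset. An event first reported after dosing but dated earlier is collected and then excluded.

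**3. What happens if it worsens after dosing?**

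| How the worsening is recorded | Onset date | Counted under 8.7.3? |
|---|---|---|
| New AE dated at the grade increase | after first dose | yes |
| Existing entry updated, onset date kept | before first dose | no |

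Sections 6.3.1 and 4.4.2 favour the first row. Section 6.1 lists time course and duration among the items to record, which allows the second row without requiring it. No section fixes the onset date. Section 4.2.1.2 also differs from 4.4.2: it sends changes from baseline to the case report form without calling them AEs.

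**4. Does the dose decision use the filter?** No. Section 6.9 applies the criteria in its Table 9, mostly CTCAE grade thresholds, for 28 days from the first PRT dose. It does not refer to 8.7.3.

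**5. What would one omission change?** Assume one patient with a worsened grade 3 or higher toxicity is left out. Intervals are exact (Clopper-Pearson) 95%. For 0/n the upper limit is 1 - 0.025^(1/n): n = 6 gives 1 - 0.541 = 45.9%, and n = 12 gives 1 - 0.735 = 26.5%.

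| Patients | Event counted | Event left out |
|---|---|---|
| 6 (one dose level) | 1/6 = 16.7% (0.4 to 64.1) | 0/6 = 0% (0 to 45.9) |
| 12 (maximum) | 1/12 = 8.3% (0.2 to 38.5) | 0/12 = 0% (0 to 26.5) |

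**The case against.** The strongest reply is that the protocol already handles this. Under 4.4.2, a toxicity found at C6D1 before dosing is medical history and a later change is an AE. Under 6.3.1, the worsening is itself an AE. Under 6.4, non-serious AEs are collected only from study drug administration, so a grade 1 diarrhoea from cycle 3 should not be an AE entry that a site could extend. Section 6.1 treats events as intermittent only when they are similar in severity, which points to a separate entry when grade 1 becomes grade 3. Most of this stands, and it is why most worsened toxicities should be counted. Two limits remain. The rule on intermittent events concerns separate episodes, not one continuing event that changes grade. And none of these sections assigns an onset date, which is the only thing 8.7.3 looks at.

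A second reply is that 4.2.1 makes any abnormality at the C6D1 assessment a screen failure, so few patients with baseline toxicity would start. Read literally, that narrows the problem. It is hard to square with 5.1, which takes account of dose modifications in cycles 1-5, or with Table 7, which allows recovery to baseline or grade 1.

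In the other direction, a reader might infer that 8.7.3 systematically removes aggravated FFX toxicity and try to size the loss. Let r be the true rate, q the share of patients with the low-grade event at entry, and f the share of worsenings filed under a pre-dose date. If worsening is equally likely in those with and without the event, the reported rate is r(1 - qf). With r = 13% (grade 3 or higher diarrhoea, section 1.8) and an assumed q = 50%, it is 13% × (1 - 0.5) = 6.5% if f = 1, and 13% if f = 0. The documents give neither q nor f, and their recording rules point towards a low f. The 13% comes from unmodified FFX in advanced disease, not from worsening after cycle 6 of the modified adjuvant regimen. The formula shows a possible range, not an expected bias.

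**Conclusion.** The gap is real but narrow. Section 8.7.3 states an exclusive, onset-only rule, and nothing in the protocol ties the onset of a worsened event to the date of worsening. Events entered afresh under 6.3.1 and 4.4.2 are counted. Those kept under a pre-dose date are not, chiefly events logged at the screening or C6D1 assessment and SAEs between consent and C6D1. Any loss favours the treatment.

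The documents do not allow its size to be estimated. It is nil if every worsening becomes a new post-dose entry. In a trial of at most 12 patients, a single omission can empty a row of the table, as the intervals above show. This assumes that the first dose is C6D1.

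The documents do not support concluding that the recommended dose and schedule is at risk, because DLTs are judged without this filter. Nor do they show that low-grade toxicity at C6D1 will be common, or that sites will keep worsened events under their pre-dose dates.

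**What to change.** In 8.7.3, define treatment-emergent as onset, or an increase in CTCAE grade over the last pre-dose assessment, on or after the first dose of study treatment, and state that this is C6D1. Tables 2 and 3 allow PRT in a later cycle, so also say whether the anchor then moves. Date a worsened event at the grade increase, with a cross-reference to 6.3.1 and 4.4.2, and bring 4.2.1.2 into line with 4.4.2. Count each subject once per preferred term, at the highest post-dose grade.

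Add one case report form instruction: for any event ongoing at C6D1, a later grade increase gets its own dated entry. This should be in place before data entry, because grade-change dates not recorded at the time may not be recoverable.

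The pre-dose grade can be taken from AE assessments already scheduled at screening and C6D1, so no visits or patients are added. The downside is that reported AE percentages may be slightly less favourable.

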HIV	Human immunodeficiency virus
HR	Hazard ratio
IFL	Irinotecan, fluorouracil (bolus), and leucovorin
IHC	Immunohistochemistry
IND	Investigational new drug
INR	International normalized ratio
IV	Intravenously
LCCC	Lombardi Comprehensive Cancer Center
LD	Longest diameter
LFT	Liver profile
LLN	Lower limit of normal
LV	Leucovorin
MRI	Magnetic resonance imaging
mOS	Median overall survival
mPFS	Median progression-free survival
NGS	Next-generation Sequencing
ORR	Overall response rate
OS	Overall survival
PCR	Polymerase chain reaction
PD	Progression of disease
PI	Principal investigator
PK	Pharmacokinetics

PO	By mouth
PR	Partial response
PRT	Proton Radiation Therapy
PS	Performance Status
PT	Prothrombin time
PTT	Partial thromboplastin time
QD	Once daily
RECIST	Response Evaluation Criteria in Solid Tumors
RFS	Recurrence-free survival
RNA	Ribonucleic acid
RP2D	Recommended Phase II Dose
RR	Response rate
SAE	Significant adverse event
SD	Stable disease
TS	Thymidylate synthase
UGT1A1	UDP glucuronosyltransferase family 1 member A1
ULN	Upper limit of normal

[figure not shown]
STUDY SYNOPSIS

Title	Phase I Study of Proton Therapy in Adjuvant Pancreatic Cancer (PROTON-PANC)
Short Title	Proton Therapy in Adjuvant Pancreatic Cancer
Protocol Number	2018-1021
Clinicaltrials.gov number:	pending
Phase	Phase I
Investigational Agents	1) Proton Beam Therapy
Indication	Resected adenocarcinoma of the pancreatic head

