4.4.6 Imaging and Evaluation

Patients will undergo a baseline tumor evaluation with imaging studies within 28 days prior to C6D1. Imaging studies should include a diagnostic CT scan of the chest, abdomen, and pelvis with PO and IV contrast (unless medically contraindicated). If a patient has an allergy to IV contrast, appropriate pre-medication can be given to prevent a contrast reaction. Patients may undergo other modalities such as an MRI instead of a CT scan at the treating physician's discretion if appropriate (such as severe allergy to CT contrast, extremity tumors, bone metastases requiring bone scans, etc.).

The first follow-up surveillance scan will occur within 14 days of the End of Treatment (EOT) visit which will be scheduled following completion of C12 or the last cycle of FFX administered. Follow-up visits including scans (CT or MRI) and blood work including CA19-9 will then occur every 3 months up to 24 months.

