4.4.10.2 Discontinuation of Individual Subjects

When a subject discontinuation from the study (without reaching a protocol-defined endpoint) is planned, the investigator will notify the PI as soon as possible (provided, in each case, subject care and safety are not compromised). When a subject discontinues the study, a final visit will be conducted (preferably prior to the initiation of another anticancer therapy). However, these procedures should not interfere with the initiation of any new treatments or therapeutic modalities that the investigator feels are necessary to treat the subject's condition. Following discontinuation of the study drug, the subject will be treated in accordance with the investigator's best clinical judgment. At the final visit, the reason(s) for the discontinuation from the study will be recorded and a physical examination, body weight, vital signs measurement, laboratory analyses, performance status, tumor assessment, and an assessment of adverse events will be performed as soon as possible after discontinuation from the study. All subjects will have one final visit, which does not need to be performed for subjects who have had a visit greater than 30 days after discontinuation of the study drugs. If a subject is discontinued from the study with an ongoing adverse event or an unresolved clinically significant laboratory result, personnel will attempt to provide follow-up until a satisfactory clinical resolution of the laboratory result or adverse event is achieved. In the event that a positive result is obtained on a pregnancy test for a subject during the study, the administration of study drug to that subject must be discontinued immediately.

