CBC with Differential _____
Comprehensive Metabolic Panel _____
CA19-9 _____
mFOLFIRINOX (Days 1-3) _____
Survival _____

End of Treatment

ECOG PS _____
Concomitant Medications Collection _____
Adverse Events Assessment _____
Vital Signs _____
Height _____
Weight _____
History and Physical Exam _____
CBC with Differential _____
Comprehensive Metabolic Panel _____
CA19-9 _____
Survival _____

Follow-Up

ECOG PS _____
Concomitant Medications Collection _____
Adverse Events Assessment _____
Vital Signs _____
Height _____
Weight _____
History and Physical Exam _____
CBC with Differential _____
Comprehensive Metabolic Panel _____
CA19-9 _____
Survival _____

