5.0 DOSAGES AND DISPENSATION OF DRUGS

5.1 FFX Administration

The study drugs are defined as 5-FU, LV, oxaliplatin, and irinotecan (FFX). Due to the infusional 5-FU, study drugs must be administered via central line (mediport, PICC, or other). Treatment cycles are every 14 days \pm 3 days (except for C6 which is 28 days in DL1 and 21 days in DL2). The study drug dosages and administration are only recommended – dosages and supportive medication can be modified at the discretion of the investigator, taking into consideration dose modifications during cycles 1-5. Per the PRODIGE 24 trial, the 5-FU bolus is omitted and irinotecan is 150 mg/m². A research infusion nurse will access the patient's line. Treatment will then be administered in the following order (substitutions for prophylactic medications are allowed at the treating investigator's discretion):

Table 5. Drug Administration

Drug	Indication	Dose/Route	Duration
Fosaprepitant	Nausea prophylaxis	150 mg IV	30 minutes
Ondansetron	Nausea prophylaxis	16 mg IV	15 minutes
Dexamethasone	Nausea prophylaxis	10 mg IV	15 minutes
Leucovorin	Treatment	400 mg/m ² IV	60 minutes
Oxaliplatin	Treatment	85 mg/m ² IV	120 minutes (can be administered simultaneously with leucovorin via a Y-connector)
Atropine	Diarrhea prophylaxis	0.5 mg IV	IV push
Irinotecan	Treatment	150 mg/m ² IV	90 minutes
5-fluorouracil	Treatment	2400 mg/m ² IV	46 hours (continuous infusion)
Pegfilgrastim on-pro	Growth factor support	6 mg SC	Administered on day 3 (after 5-fluorouracil pump is unhooked)

The patient will return to the research infusion clinic after 46 hours for disconnection of the 5-FU infusional pump and administration of pegfilgrastim on-pro. Use of growth factor support is highly recommended but is at the discretion of the investigator. Alternatively, pegfilgrastim 6 mg SC can be administered on day 4 (if not using on-pro administration).

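### Section 8.7.3 leaves AEs starting more than 30 days after treatment (probably last FFX dose, but not stated) out of the AE tables despite AE assessments to 24 months, and the relatedness wording does not cover PRT

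*Combined protocol and SAP*

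**What the plan says.** **Analysis window.** 8.7.3 counts events from the day of the first dose of study drug and then sets an upper limit: "Analyses will not include those that have an onset greater than 30 days after the treatment". This applies to AEs and SAEs alike. 6.4 ends collection of AEs 30 days after study drug is discontinued; SAEs are collected from consent, with no separate end date.

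**Schedule.** Tables 2 and 3 mark AE assessment in the follow-up column, and the follow-up part of the Table 4 checklist lists "Adverse Events Assessment". Under 4.4.6 the EOT visit is "scheduled following completion of C12 or the last cycle of FFX administered", and follow-up visits "will then occur every 3 months up to 24 months". 4.4.2 says that at each visit "any changes from baseline will be recorded as an adverse event". The safety endpoint in 8.3.1 gives no time limit.

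**Attribution.** The synopsis has one entry under investigational agents: "1) Proton Beam Therapy". Section 5.1 reads: "The study drugs are defined as 5-FU, LV, oxaliplatin, and irinotecan (FFX"; PRT is not included. The causality scale in 6.3.4 and the relatedness summaries in 8.7.3 and 8.7.4 all refer to study drug. 8.7.1 and 8.7.2 name both FFX and PRT, but for overall safety and exposure rather than attribution.

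**The concern.** Safety of placing PRT within adjuvant FFX is a co-primary objective, and the rationale in 1.4 expects fewer acute and long-term toxicities from protons than from conventional photon IMRT. A 30-day limit on onset means the AE tables cannot describe the long-term part, although the visits at which such events would be found are already planned. If causality is recorded only against FFX, the tables also cannot say which events were attributed to the treatment under test.

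The limit sits in 6.4 as well as 8.7.3. Changing the analysis section alone would not recover late events, because collection of new non-serious AEs stops at the same point.

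**Working it through.** The plan gives no figure to reproduce, so the check is calendar arithmetic on its own schedule.

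**Inputs**
- PRT on days 15-19 of a 28-day cycle (DL1) or days 8-12 of a 21-day cycle (DL2): 4.1, 8.5.
- Other cycles 14 days; FFX on days 1-3: 4.1, 8.5.
- PRT may be given in any of cycles 6 to 11: footnote b, Tables 2 and 3.
- DLT window: 28 days from the first fraction, 6.9.
- EOT is day 1 of the last FFX cycle: footnote d, Tables 2 and 3.
- Assumptions: no delays, 3 months = 91 days, last FFX on day 3 of the last cycle, and *the treatment* means FFX.

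**Cut-off for a 12-cycle completer, PRT in cycle 6** (day 1 = C6D1)
- DL1: C7D1 = 29; C12D1 = 29 + 5 × 14 = 99; last FFX = 101; cut-off = 101 + 30 = 131. Last fraction = 19, so 131 − 19 = **112 days**.
- DL2: C7D1 = 22; C12D1 = 22 + 70 = 92; last FFX = 94; cut-off = 124. Last fraction = 12, so 124 − 12 = **112 days**.

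**Same patient, PRT in cycle 11** (day 1 = C11D1)
- DL1: C12D1 = 29; last FFX = 31; cut-off = 61; 61 − 19 = **42 days**.
- DL2: C12D1 = 22; last FFX = 24; cut-off = 54; 54 − 12 = **42 days**.

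Footnote c of Table 3 puts C7D1 at C6D15 in DL2, which does not agree with a 21-day cycle and must be reconciled. On the footnote's day, the DL2 figures become 105 and 35.

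**FFX stopped for good after C6D3, PRT still given in cycle 6**
- Cut-off = 3 + 30 = C6D33.
- DLT window closes at 15 + 28 = C6D43 (DL1) or 8 + 28 = C6D36 (DL2).
- AE collection under 6.4 could therefore end 10 or 3 days before the DLT window does.

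**Position of the follow-up visits**
- With EOT on day 1 of the last cycle: (1 + 91) − (3 + 30) = 59 days past the cut-off, whichever cycle is last.
- With EOT after C12 is complete (4.4.6), taken as C12D15: 59 + 14 = 73 days past.
- If the 24 months run from EOT, there are 24 / 3 = 8 such visits, all after the cut-off.

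The cut is on onset, not visit date. With EOT on day 1 of the last cycle, onset in roughly the first 32 of the 91 days before the first follow-up visit (131 − 99 = 124 − 92 = 32) is inside the window and is counted when reported there.

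**The case against.** A 30-day treatment-emergent window is an ordinary design choice, and several stronger readings go too far.

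- **That the anchor is open and two rival AE tables could result.** A reader might take *the treatment* as PRT, which would stop the analysis at 19 + 30 = C6D49 (DL1) or 12 + 30 = C6D42 (DL2), both C8D7. The documents do not favour this. 6.4 counts 30 days from study drug, 8.7.4 counts deaths from the last dose of study drug, EOT is tied to the last FFX cycle, and 4.4.10.2, which says "All subjects will have one final visit", waives it by reference to 30 days after the study drugs. Last FFX dose is the likely anchor; it needs only to be stated.
- **That all AE data from follow-up are discarded.** They are not, since onset decides. The follow-up columns may also be meant for existing events, which 4.4.5 and 6.1 require to be followed to resolution. 4.4.2 is a weak witness as well: the Medical History row is marked at screening only, although history and physical examination is marked at follow-up. And 8.3.1 is silent on time rather than in conflict.
- **That PRT toxicity is ignored.** 8.7.1 and 8.7.2 name PRT, 4.4.1 records examination findings as AEs from the first PRT doses, and most DLT items need no attribution. Calling only FFX study drug may be loose wording. For some SAEs 6.3.4 requires another cause, where PRT could be entered. The CRF is not in the documents, so whether it has a PRT field cannot be checked.
- **That the RP2D is at risk.** DLTs have their own window, tied to PRT.

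Late deaths are summarised without limit, laboratory and vital-sign changes in 8.7.1 have no cut-off, and SAEs go to the IRB whatever their cause. What stands is that none of these provisions tabulates late non-fatal AEs, and none sets out relatedness to PRT.

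**Conclusion.** The point holds in a limited form. As written, new non-fatal AEs and SAEs starting more than 30 days after treatment, most plausibly the last FFX dose, are left out of the AE tables although AE assessment is scheduled to 24 months. For a 12-cycle completer without delays, coverage after the last fraction runs from 42 to 112 days depending on the cycle in which PRT is given, so 112 should not be read as general. With FFX stopped after C6D3, AE collection can end before the DLT window. The documents give no late-event rate, so the number of events lost cannot be estimated.

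The attribution gap is real in the wording but may not reflect intent. The effect is on the co-primary safety description, not on dose-level decisions. It is worth correcting because the correction is cheap.

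**What to change.** 1. **5.1:** add a term *study treatment*, meaning FFX plus PRT, and use it in 6.3.4, 6.4 and 8.7. A new term avoids altering by accident the study-drug clauses in 4.4.10.2 and 6.6, which the sponsor should check.
2. **6.3.4, 8.7.3, 8.7.4:** record and report relatedness to FFX and to PRT separately.
3. **6.4, 8.7.3:** state the anchor as the later of the last FFX dose and the last PRT fraction, with AE collection not ending before the DLT window. In the early-stop case the cut-off moves from C6D33 to C6D49 (DL1) or C6D42 (DL2), past the window's end at C6D43 or C6D36.
4. **8.7.3:** keep the 30-day table and add a listing, by dose level, of later-onset AEs (for example grade 3 or higher, or PRT-related) from the scheduled visits. With at most 12 patients a listing is enough.
5. **6.4 with 4.4.2 and Tables 2 to 4:** say whether follow-up AE assessment covers new events or only existing ones, and make the sections agree.

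The cost is wording in a few sections, an attribution field if the CRF lacks one, one listing and slightly more data entry in follow-up, with no new visits. Attribution between FFX and PRT will sometimes be uncertain, since every patient treated with PRT also receives FFX.
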